## 15.12.2023 THE EFFECT OF PREOPERATIVE ANXIETY LEVEL ON POSTOPERATIVE SORE THROAT IN TYMPANOPLASTIES

### INTRODUCTION

Tympanoplasty is the general name given to operations in which the defect in the tympanic membrane is repaired with a connective tissue graft to correct the pathology in chronic otitis media and its sequelae (1). The pathology in the middle ear and mastoid system may vary from a central tympanic membrane perforation in which the mucosa and ossicles in the middle ear are completely dry to cholesteatoma in which the entire membrane and ossicles in the middle ear are destroyed and sometimes complications such as facial paralysis, labyrinth fistula, meningitis and brain abscess are observed. A simple myringoplasty in which only the perforated eardrum is repaired is the simplest type of tympanoplasty. Radical mastoidectomy is the method in which the middle ear and outer ear mastoid system are made into a single cavity (1).

The word "anxiety" is derived from the Indo-Germanic word "anh" which means "pressing tightly, strangling, distress and anxiety". In Turkish, it is used as "bun", "overwhelm", "boredom" or "unpleasant excitement". Anxiety, which decreases the efficiency of the person and causes problems in social relations, and in which physical symptoms such as trembling, heart palpitations, and a feeling of dryness in the mouth occur, is considered pathological (2). Anxiety is an emotional state defined as a restless feeling whose source is usually uncertain. It may cause abnormal haemodynamic changes as a result of sympathetic, parasympathetic and endocrine stimulation. Anxiety and fear increase during the time when patients are waiting for the time when they will undergo surgery (3). It is important to inform the patient about anaesthesia and surgery in the preoperative preparation process. Anxiety negatively affects surgery, anaesthesia maintenance and postoperative recovery. Elimination of anxiety in the preoperative preparation period is important to improve the quality of postoperative recovery and to reduce costs (4). Scales such as State-Trait Anxiety Inventory (STAI: State-Trait Anxiety Inventory), APAIS, Hospital Depression and Anxiety Scale (HADS), and Beck Anxiety Scale (Beck Anxiety Scale), which measure trait and state anxiety separately, can be used to determine anxiety levels.

Postoperative sore throat (POBA) is a common complication of general anaesthesia. Although it is less harmful than other complications, it decreases postoperative comfort of patients and may prolong hospital stay. After intubation, patients may experience complications such as hoarseness, dysphagia, cough and dry throat with POBA (5). The incidence due to tracheal intubation has been reported to be 62% and it is thought to be caused by injury with laryngoscopy or damage to the tracheal mucosa due to cuff pressure (6). Sore throat in the postoperative period negatively affects patient comfort and may lead to an unpleasant anaesthetic experience.

This study aimed to reveal the relationship between preoperative anxiety level and postoperative sore throat and other complications in patients undergoing tympanoplasty.

## MATERIALS AND METHODS

A total of 80 volunteer patients who will undergo tympanoplasty under general anaesthesia under elective conditions will be included in the study according to the inclusion and exclusion criteria.

Inclusion criteria:

- 1- Intubated under general anaesthesia
- 2- Surgical time  $\geq$ 30 minutes and  $\leq$  4 hours
- 3- 18-65 years old
- 4- ASA I-II patients will be included in the study

Exclusion criteria:

- 1- Those who are unable to read and understand the consent form and anxiety assessment scale
- 2- Previous vocal cord surgery
- 3- Previous head and neck surgery
- 4- Pregnant women
- 5- Patients using steroids
- 6- Operation time  $<$ 30 minutes and  $>$ 4 hours
- 7- Antidepressant drug users and patients diagnosed with psychiatric illness will be excluded from the study.

Anesthesia Administration:

Demographic data (age, gender, height, weight, body mass index (BMI) and ASA classification will be recorded preoperatively. The trait and state anxiety scale (STAI-T and STAI-S) will be administered at the preoperative visit. Standard anaesthesia monitoring (electrocardiogram-ECG, noninvasive blood pressure-NIBP, pulse oximetry-SPO2, temperature, EtCO2- End Tidal Carbon Dioxide), neuromuscular monitoring (TOF) will be performed before anaesthesia induction. These data will be recorded at 5 minute (min) intervals from the beginning to the end of the operation. A vascular access of appropriate width will be opened and 10 ml/kg balanced crystalloid fluid infusion will be started. Lidocaine 1 mg/kg, fentanyl 1 mg/kg propofol 2-3 mg/kg and rocuronium 0.6 mg/kg will be administered intravenously (IV). Then, when the Train of four rate (TOFR) response is zero, orotracheal intubation will be performed with Macintosh bleyd 3 or 4 by selecting straight tubes with an inner diameter of 8.0-8.5 mm for male patients and 7-7.5 mm for female patients. (In case of neuromuscular blocker requirement, rocuronium 0.1 mg/kg IV will be administered additionally. Endotracheal tube (ETT) cuff pressure will be adjusted to 20-30 cmH2O with a cuff manometer. ETT cuff pressure will be measured at 20 minute intervals and recorded in the file. Anaesthesia maintenance will be performed with 0.5 L/min fresh gas flow, oxygen concentration with inspiratory oxygen level between 40-45, sevoflurane with a minimum alveolar concentration (MAK) of 1.0. Mechanical ventilation will be performed with Volume-Auto Flow mode with EtCO2 between 35-40 mmHg. Analgesia maintenance will be provided with remifentanil infusion (0.6-15 mcg/kg/hour). In case of ( $\pm$ ) 15% change in the haemodynamic parameters of the patient compared to the baseline values, remifentanil (Rentanil 2 mg-VEM drug) infusion dose will be intervened by increasing and decreasing at the specified intervals and the amount consumed intraoperatively at the end of the operation will be recorded. Hypotension will be defined

as hypotension when systolic arterial pressure decreases by 30% compared to baseline. In the treatment, 250 ml of 0.9% NaCl rapid infusion will be administered first. If no response is obtained, 10 mg ephedrine IV (Ephedrine Hydrochloride 0.05 g/1 ml-Osel drug) will be given. When bradycardia occurs (heart rate  $\leq$ 50 beats/min), atropine 0.5 mg IV (Atropine Sulphate Onfarma 0.5 mg/ml) will be administered.

Paracetamol 10 mg/kg and tramadol 1 mg/kg will be administered before the operation is terminated. Fresh gas flow will be increased to 8 L/min at the end of the operation. Sugammadex 4 mg/kg will be administered IV to terminate neuromuscular blockade. When TOFR is 0.9, the patient will be extubated and transferred to the postoperative recovery unit (PACU). Patients with Aldrete score  $\geq$  9 will be transferred from PACU to the ward.

The time from skin incision until the end of the surgical procedure will be recorded as "Operation Time". The time between the termination of sevoflurane (Sevorane 100% inhalation solution) flow and extubation will be recorded as "Extubation Time", and the time between anaesthesia induction and extubation will be recorded as "Anaesthesia Time". The time between the patient's admission to the PACU and discharge to the ward will be recorded as "Recovery Time".

Postoperative complaints of sore throat, hoarseness, cough, nausea and vomiting will be recorded at 0, 2, 4 and 24 hours using numerical rating scales (NRS). After the end of follow-up, the patient will be divided into two groups according to anxiety level (7). The intraoperative data and postoperative complication status of the volunteers will be followed up by an anaesthesiologist who is not aware of the results of the anxiety rating scale and recorded in their files.

All patients will be asked whether they have sore throat at 0, 2, 4, 12 and 24 hours postoperatively. Patients will be asked to give a score between 0-10 for sore throat.

All patients will be asked whether they complain of hoarseness at 0, 2, 4, 12 and 24 hours postoperatively. Patients will be asked to give a score between 0-1-2-3 for hoarseness.

All patients will be asked about cough at 0, 2, 4, 12 and 24 hours postoperatively. Patients will be asked to give a score between 0-1-2-3 for cough complaint.

All patients will be asked about nausea and vomiting at 0, 2, 4, 12 and 24 hours postoperatively. Patients will be asked to give a score between 0-1-2-3 for nausea and vomiting.

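### Does the 30-minute to 4-hour limit on surgery make eligibility depend on something known only after anxiety has been measured?

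*Protocol*

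**What the plan says.** All of this is in the Protocol, MATERIALS AND METHODS.

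- Recruitment looks forward: "A total of 80 volunteer patients who will undergo tympanoplasty under general anaesthesia under elective conditions" are to be included according to the listed criteria.
- Inclusion criterion 2 reads "Surgical time $\geq$ 30 minutes and $\leq$ 4 hours". Exclusion criterion 6 reads "Operation time $<$ 30 minutes and $>$ 4 hours". Neither carries a qualifier such as planned or expected.
- Inclusion criterion 1 reads "Intubated under general anaesthesia", a condition that likewise cannot yet be met by someone awaiting surgery.
- Under Anesthesia Administration, "The trait and state anxiety scale (STAI-T and STAI-S) will be administered at the preoperative visit". Induction and intubation follow.
- Two relevant times are then recorded. For Operation Time: "The time from skin incision until the end of the surgical procedure will be recorded as" that variable. For Anaesthesia Time: "the time between anaesthesia induction and extubation will be recorded as" that variable.
- Anxiety groups are formed after follow-up ends, and intraoperative and postoperative data are recorded by an anaesthesiologist who does not know the anxiety scores.

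The protocol does not say what happens to an enrolled patient whose operation falls outside the window.

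**The concern.** An eligibility criterion should be decidable when the patient enters the study. Exclusion 6 uses the term that the protocol later defines as a measured interval, so the plain reading is that eligibility is confirmed only when the operation ends. By then the patient has consented, completed both anxiety scales and been intubated.

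Two things could be at stake. The first is numbers: patients dropped late either reduce the 80 or have to be replaced. The second is selection on a variable that arises after the exposure. If anxious patients tended to have longer or shorter operations, and duration were also related to sore throat, cutting off the extremes could distort the association under study. The Introduction gives this some colour by saying that "Anxiety negatively affects surgery, anaesthesia maintenance and postoperative recovery".

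**Working it through.** **1. The two criteria side by side.** Inclusion 2 accepts durations t with 30 ≤ t ≤ 240 minutes. Read literally, exclusion 6 removes t < 30 and t > 240 together, which no duration satisfies (0 of the whole-minute values from 1 to 399). With the conjunction read as *or*, it is the exact complement of inclusion 2. The two criteria then say the same thing, and the slip changes nobody's eligibility because inclusion 2 already sets the window.

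**2. When measured time would become known.** A case over 4 hours is identified once 4 hours have passed. A case under 30 minutes is identified when surgery ends. Both moments come after the anxiety scales and intubation, but before extubation and so before any sore-throat score. Scores would exist for an excluded patient only if the check were made later from the file.

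**3. Effect on numbers.** The plan's figure of 80 comes with no power, effect size or dropout rate in the protocol, so there is nothing to reproduce. The share p of operations outside the window is also not given; the values below are assumptions.

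- Left if not replaced: 80(1 − p).
- Enrolled to keep 80: 80/(1 − p), rounded up.
- Detectable difference: two-sample t-test, two equal groups, two-sided 5%, 80% power (all assumed).
- Power at 0.634 SD: same test.

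| p | Left of 80 | Enrol to keep 80 | Detectable difference (SD), no replacement | Power at 0.634 SD, no replacement |
|---|---|---|---|---|
| 0 | 80 | 80 | 0.634 | 80.0% |
| 2.5% | 78 | 83 | 0.643 | 78.9% |
| 5% | 76 | 85 | 0.651 | 77.9% |
| 10% | 72 | 89 | 0.670 | 75.6% |
| 15% | 68 | 95 | 0.690 | 73.1% |

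For example, 80 × 0.975 = 78, and 80/0.975 = 82.05, rounded up to 83. The chance that at least one of 80 falls outside is 1 − (1 − p)^80: 33% at p = 0.5% and 87% at p = 2.5%.

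The last two columns apply only if the 80 are counted before late exclusions. The recruitment sentence ties the 80 to the criteria, so the enrolment column is the more natural reading, and under it neither N nor power is lost.

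**4. Bias.** Distortion requires duration to be related to anxiety and also to sore throat. The Introduction's remark on anxiety and surgery does not mention duration. Its account of sore throat points to laryngoscopy and cuff pressure, again without duration. No size or direction can be derived from the document.

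**The case for a change.** The best case for acting is that eligibility belongs in the protocol, that planned and measured time give different study populations, and that the text does not choose between them. A word in each criterion would settle it, and a count of out-of-window patients could be taken from the Operation Time already recorded. The ambiguity stands, and so does the general caution about selecting on a post-exposure variable.

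The rest carries less weight. The strict reading is applied unevenly: one must forgive the wrong conjunction in exclusion 6 and the past participle in inclusion 1 as loose drafting, yet hold the absence of one adjective to the letter. Inclusion 2 speaks of surgical time, which is not defined, and the definition of Operation Time belongs to a list of recorded variables that is not tied to the criteria. The forward-looking recruitment sentence favours expected duration.

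Keeping very short and very long operations in the main analysis is not plainly better either. A duration window limits the spread in intubation time, which is a legitimate aim when the outcome is sore throat after intubation. Nor is screening on planned time wholly free: the protocol records actual times only, so a planned duration would be a new item. How out-of-window patients enter the analysis sets is something a SAP, not shown here, commonly covers.

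**Conclusion.** No change follows. What remains is one unstated adjective and one clerical slip, and either reading leaves a sound study: planned time means routine screening, and measured time means a cohort restricted to 30 minutes to 4 hours. With replacement, the cost of the measured reading is 3 to 15 extra enrolments at an assumed 2.5% to 15% outside the window. Without replacement, the detectable difference rises by 0.009 to 0.056 SD (0.643 − 0.634 and 0.690 − 0.634), assuming equal groups. An assumed 1:3 split of the anxiety groups with nobody lost would already give about 0.73 SD, so the balance of the groups could matter more than this. If no operation falls outside the window, nothing is lost.

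No bias is shown. The exclusion can be decided before any sore-throat score is taken, and the anaesthesiologist recording the data does not know the anxiety results. That makes discretionary exclusion linked to anxiety unlikely, although it does not rule out selection through duration itself. The conclusion would need revisiting only if a substantial share of operations fell outside the window and that share differed between anxiety groups; the recorded Operation Time would show this.

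### The fentanyl induction dose is printed as 1 mg/kg (1000 mcg/kg), a 1000-fold unit error if 1 mcg/kg was meant and the source document also reads mg

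*Protocol*

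**What the plan says.** The Anesthesia Administration part of Materials and Methods sets the induction regimen in one sentence: "Lidocaine 1 mg/kg, fentanyl 1 mg/kg propofol 2-3 mg/kg and rocuronium 0.6 mg/kg will be administered intravenously (IV". All four drugs in it carry the same unit, mg/kg. The sentence is current, operative text and has no exception for any patient. Its scope is the whole study: "A total of 80 volunteer patients who will undergo tympanoplasty under general anaesthesia under elective conditions will be included".

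This is the only mention of fentanyl in the document. The same part of the text doses a second opioid in micrograms: "Analgesia maintenance will be provided with remifentanil infusion (0.6-15 mcg/kg/hour".

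**The concern.** A dose of 1 mg/kg is 1000 mcg/kg. The protocol states no intended fentanyl dose against which to test this, so calling it a unit error rests on an assumption: that an induction bolus of fentanyl is meant in micrograms. On that assumption the line is wrong by about three orders of magnitude, in an intravenous dosing instruction that applies to everyone enrolled.

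What is at stake is safety as written. A dosing line in a protocol should not depend on the reader noticing that it is wrong and overriding it. The trial's inference is not at stake: the line applies to all patients alike, and the grouping comes later ("After the end of follow-up, the patient will be divided into two groups according to anxiety level (7").

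**Working it through.** No sample size, power or error rate is involved. The check is a unit conversion, followed by a reading of the surrounding text.

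**Inputs from the protocol (Materials and Methods)**
- Fentanyl at induction: 1 mg/kg, intravenous.
- Remifentanil maintenance: 0.6 to 15 mcg/kg/hour.
- Longest permitted operation: 4 hours.

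**Assumptions, not in the protocol**
- Body weights of 50, 70 and 100 kg, for illustration. Weight is recorded, but no range is given.
- Intended fentanyl dose of 1 mcg/kg, with 1 to 5 mcg/kg as the range.

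**Step 1: conversion.** 1 mg/kg × 1000 mcg/mg = 1000 mcg/kg.

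**Step 2: absolute dose**

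| Assumed weight | As printed (1 mg/kg) | If 1 mcg/kg was meant | Ratio |
|---|---|---|---|
| 50 kg | 50 mg | 0.05 mg (50 mcg) | 1000 |
| 70 kg | 70 mg | 0.07 mg (70 mcg) | 1000 |
| 100 kg | 100 mg | 0.10 mg (100 mcg) | 1000 |

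**Step 3: if the numeral is wrong as well as the unit.** The ratio is 1000 divided by the intended dose in mcg/kg: 1000/1 = 1000, 1000/2 = 500, 1000/5 = 200. The printed dose is at least 200 times too high across the assumed range.

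**Step 4: scale against the other opioid infusion.** The highest remifentanil rate held for 4 hours gives 15 × 4 = 60 mcg/kg. The single printed fentanyl bolus is 1000/60 ≈ 17 times that total. These are different drugs, so this is a comparison of mass and not of potency. It shows that the printed bolus is large beside the rest of the regimen, but it does not establish the intended unit.

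**Step 5: could the unit be an artefact of reading the PDF?** In the text as shown:
- Fentanyl appears once, so there is no second statement to compare.
- Eight doses are in mg/kg: lidocaine, fentanyl, propofol, rocuronium (two doses), paracetamol, tramadol and sugammadex.
- One dose is in micrograms (remifentanil), spelled mcg. There is no micro sign.
- Seven other special symbols survived: ≥ twice, ≤ twice, and ±, < and > once each (2 + 2 + 1 + 1 + 1 = 7).

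The spelling mcg is the most useful of these facts, because authors who write micrograms that way would have had no micro sign to lose. The other counts are weaker evidence.

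**The case against.** The strongest objection is that the error may not be the authors'. A micro sign misread as the letter m would produce exactly the printed line. Counting no micro signs is then circular, and the symbols that survived do not resemble letters, so their survival says little. The spelling mcg occurs only once. All of this is fair. It is why an artefact cannot be excluded and why confidence is medium. The spelling still tips the balance the other way.

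A second possibility is translation. The English text appears to have been translated, and a local-language version used by staff could be correct. The documents cannot settle that. It would still leave the English protocol wrong and in need of correction.

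Third, the protocol contains no correct fentanyl value, and it has no rule that opioids are dosed in micrograms, since tramadol is given in mg/kg. This stands. The microgram reading is an assumption and is labelled as one. The size of the discrepancy is large across the whole assumed range.

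Finally, fentanyl is not the exposure under study, the comparison is unaffected, and an anaesthetist would be expected to recognise the figure as a misprint. The first two points are accepted. The third is general knowledge, not something the protocol provides for, and it is not a reason to leave a wrong dose in a written instruction.

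**Conclusion.** The concern holds, conditionally. As printed, the protocol orders 1000 mcg/kg of fentanyl intravenously for all 80 patients. That is 1000 times too high if 1 mcg/kg was meant, and 200 to 1000 times too high over an assumed intended range of 1 to 5 mcg/kg.

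The conclusion rests on two things the document cannot confirm: that the source also reads mg, and that micrograms were intended. If the source reads mg, the line must be corrected. If it reads mcg, the point lapses.

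**What to change.** Check the line against the source document and, if there is one, the original-language version.
- If the source reads mcg, no change is needed.
- If it reads mg, the investigators confirm the intended fentanyl dose, correct the unit (presumably to 1 mcg/kg, which is an assumption) and notify the ethics committee.
- If only the English version is wrong, correct that version. Whether a notification is then needed depends on which version the committee approved.

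The check takes minutes, and the correction is one line plus the notification.

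### Does the study need the number of intubation attempts recorded, given that the protocol cites laryngoscopy injury as a suspected cause of sore throat?

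*Protocol*

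**What the plan says.** The Introduction, writing of sore throat after tracheal intubation, reports that "it is thought to be caused by injury with laryngoscopy or damage to the tracheal mucosa due to cuff pressure". It ends with the aim: to show how preoperative anxiety relates to postoperative sore throat and other complications in tympanoplasty.

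Materials and Methods, under Anesthesia Administration, treats the two causes differently.

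- **Cuff pressure** is kept within 20-30 cmH2O, and "ETT cuff pressure will be measured at 20 minute intervals and recorded in the file".
- **Laryngoscopy** is standardised: "orotracheal intubation will be performed with Macintosh bleyd 3 or 4", with a tube range for each sex, and intubation takes place "when the Train of four rate (TOFR) response is zero". No attempt count, laryngoscopic view or difficulty grade is named as a record.

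Other intraoperative records are listed individually. They include monitoring values every 5 minutes, remifentanil ("the amount consumed intraoperatively at the end of the operation will be recorded") and several time intervals, for example "The time from skin incision until the end of the surgical procedure will be recorded as" the operation time. The protocol also has a general provision: "The intraoperative data and postoperative complication status of the volunteers will be followed up by an anaesthesiologist" who does not know the anxiety results, and entered in the files. The exclusion list includes earlier vocal cord surgery and "Previous head and neck surgery".

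**The concern.** The protocol cites two causes of its title outcome and names a measurement for only one. The anxiety groups are formed from questionnaire scores, not by randomisation, so nothing guarantees that airway trauma is balanced between them. If intubation happened to be harder in one group, a difference in sore throat could partly reflect that, and the items named would not show it. Standardising the blade, the tube and the relaxation condition does not reveal how many attempts each patient needed. Nor can this be left to an analysis plan, because a variable that was never collected cannot be recovered later. At stake would be how a difference in sore throat, or its absence, is interpreted.

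**Working it through.** **Step 1. Is the omission real?** Yes. The named records are demographics and ASA class, the two STAI scales, 5-minute monitoring, cuff pressure, remifentanil consumed, the operation, extubation, anaesthesia and recovery times, and the postoperative complaints. None is an attempt count. Anaesthesia time runs from induction to extubation, so it cannot isolate intubation.

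**Step 2. Does the omission contradict anything in the protocol?** Set side by side, the sentence on causes reports what is thought in general about sore throat after intubation, while the aim asks about the relationship between anxiety and sore throat. The first does not commit the study to measure each mechanism. The second does not ask for the relationship to be divided by mechanism. The protocol says nothing about repeat attempts, difficult airways or how attempts relate to injury. An attempt count would in any case be a proxy for laryngoscopy injury, since a single laryngoscopy can injure.

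**Step 3. Would leaving it out bias the stated comparison?** The order of events is:

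1. STAI at the preoperative visit;
2. intubation;
3. sore throat from 0 to 24 hours.

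Attempts follow the anxiety measurement and cannot have caused the score. If anxiety affected them, they would lie on the pathway, and the overall relationship would be estimated correctly without them. If they were unrelated to anxiety, omitting them would add scatter but no bias. They would matter as a confounding route only if something present beforehand raised both anxiety and the difficulty of intubation. The protocol suggests no such factor, and it narrows the setting: elective ASA I-II patients, the airway-related exclusions, set equipment and full relaxation.

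**Step 4. What could a table of attempts by group show?** The protocol gives no repeat-attempt rate and no group split. Assume 5% to 20% with a repeat attempt and groups of 40 and 40, with 20 and 60 as an alternative.

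- Patients with a repeat attempt: 80 × 0.05 = 4; 80 × 0.20 = 16.
- Half-width of the 95% CI with equal rates: 1.96 × √[p(1−p)(1/n₁ + 1/n₂)].
  - 40 v 40: p = 0.05 gives 1.96 × √(0.0475 × 0.05) = 9.6 points; p = 0.20 gives 1.96 × √(0.16 × 0.05) = 17.5 points.
  - 20 v 60: 11.0 and 20.2 points.
- Selected splits, with Newcombe 95% CI and Fisher's exact p:

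| Repeat attempts | Difference (points) | 95% CI | p |
|---|---|---|---|
| 4/40 v 0/40 | 10 | -0.6 to 23.1 | 0.116 |
| 10/40 v 6/40 | 10 | -7.7 to 27.1 | 0.40 |
| 12/40 v 4/40 | 20 | 2.3 to 36.6 | 0.048 |
| 4/20 v 0/60 | 20 | 6.6 to 41.6 | 0.003 |

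In equal groups at the low end of the range, the most extreme split possible still has an interval that includes zero. At the high end, a 20-point gap only just excludes it. With 20 and 60 the most extreme split, with all four repeats in the smaller group, would stand out. So the table could flag a gross imbalance in some configurations and could not rule out a moderate one. These figures concern the table of attempts only. They say nothing about the effect on sore throat.

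**The case for a change.** The strongest case for the concern is that the facts are right, the entry costs one field in each of 80 files, and it can only be obtained at the time. Describing attempts by group would be valid whether they act as a mediator or a confounder. Difficult intubation is not an exclusion criterion, so attempts may vary. The general reference to intraoperative data does not ensure that every file holds the same entry, particularly as other items are named one by one.

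Much of this stands. The item is not named, the general wording may or may not cover it in practice, and an analysis plan could not recover it. A confounding route can also be imagined: a patient who knows of an earlier difficult intubation may be more anxious and may need more attempts again. Nothing in the protocol indicates that this occurs or how often.

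What does not follow is that the plan is wrong. The argument shows that a further descriptive table would be possible. It does not show that the anxiety comparison would be mistaken or worse without it. The same reasoning would apply to any other unlisted influence on sore throat.

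**Conclusion.** The concern does not hold. Attempts are indeed not a named record, but on this point the protocol states nothing wrongly, does not contradict itself and fixes nothing badly. Its sentence on causes is background, its aim is the overall relationship, and attempts come after the anxiety measurement. Followed as written, the plan answers its stated question no worse for lacking this item.

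The size of any effect on the sore throat comparison cannot be derived from the document. The only figures available describe an optional table of attempts. With 4 to 16 repeat attempts among 80 patients and equal groups, that table would have a half-width of about 10 to 18 points, and would be more of a safeguard against gross imbalance than a basis for adjustment. This rests on the assumed 5% to 20% rate and the assumed split. The conclusion on bias rests on the order of events and on the absence of any factor in the protocol that links anxiety to difficulty of intubation. A team that wants the extra entry may add it as a preference, but the main result does not require it.

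### The only stated use of the anxiety score is a two-group split; keeping it continuous would recover information from the same 80 patients if the relation is roughly linear

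*Protocol*

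**What the plan says.** The aim, at the end of the Introduction, concerns a relationship with anxiety level: "This study aimed to reveal the relationship between preoperative anxiety level and postoperative sore throat and other complications in patients undergoing tympanoplasty". Under Materials and Methods the sample is fixed at 80 patients, with no derivation. Under Anesthesia Administration, "The trait and state anxiety scale (STAI-T and STAI-S) will be administered at the preoperative visit", so two questionnaire scores will exist for each patient. Later in that section comes the one stated use of them: "After the end of follow-up, the patient will be divided into two groups according to anxiety level (7"; the 7 is a citation.

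The scale is otherwise mentioned only in the exclusion of patients who cannot read it and in the blinding of the follow-up anaesthesiologist to its result. No correlation, regression or other use of the score as a graded quantity is described, and no analysis is called primary. Sore throat is scored 0-10; hoarseness, cough, and nausea and vomiting are scored 0-3.

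**The concern.** The question is about degree of anxiety, the measurement is graded, and the stated plan reduces it to two categories. Patients just above and just below the cut are treated as different, while patients far apart on the same side are treated as identical. With a sample of 80, information already collected is discarded. If the split is the main analysis and the outcome changes roughly linearly with anxiety, power and precision are lost for sore throat and for the other complications named in the aim.

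Forming the groups after follow-up is not itself a source of bias: anxiety is measured before surgery and the follow-up assessor is blinded to it. A smaller point is that the sentence does not say whether STAI-S or STAI-T defines the groups, or at what cut-off. Reference 7 may supply both.

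**Working it through.** **Inputs.** From the protocol: n = 80, and a two-group split of a STAI score. Assumed, because the protocol does not give them: two-sided 5% level, correlation r = 0.30 (range 0.20 to 0.40), group shares, shape of the score distribution, no dropout. The protocol's 80 cannot be reproduced, since none of its inputs is stated; it is taken as given.

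**Information kept by a split under a linear relation**, with share p in the upper group and φ the standard normal density:

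- normal score: φ(z_p)² / [p(1−p)]; at the median 0.3989² / 0.25 = 0.637
- uniform score: 3p(1−p); at the median 3 × 0.25 = 0.75

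The effective sample size is 80 times the share kept.

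**Power** by Fisher z: Φ(√77 · atanh(r) − 1.96), with r multiplied by the square root of the share kept when the score is split. Continuous, r = 0.30: 8.775 × 0.3095 − 1.960 = 0.756, giving 77.5%.

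| Upper group | Kept (normal / uniform) | 80 patients act like | Power at r = 0.30 |
|---|---|---|---|
| 50% | 0.637 / 0.750 | 50.9 / 60.0 | 57.2% / 64.6% |
| 30% | 0.576 / 0.630 | 46.1 / 50.4 | 52.9% / 56.8% |
| 20% | 0.490 / 0.480 | 39.2 / 38.4 | 46.4% / 45.7% |
| 10% | 0.342 / 0.270 | 27.4 / 21.6 | 34.3% / 28.1% |

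To match 80 patients analysed continuously, a median split would need 80/0.637 = 125.7 (normal) or 80/0.75 = 106.7 (uniform), that is 126 or 107 patients. The median-split range is not a ceiling: a right-skewed score (gamma with shape 4, skewness 1) keeps 0.594, a loss of 41%.

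**Other correlations** (normal score, median split), continuous against split: r = 0.20, 42.8% against 29.2%; r = 0.25, 61.1% against 42.6%; r = 0.35, 89.4% against 71.1%; r = 0.40, 96.1% against 82.7%.

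**Simulation**, 20,000 trials of 80 patients per setting, normal score, r = 0.30. With a normal outcome, power is about 78% continuous and 58% at a median split. With an assumed skewed 0-10 outcome and r on the latent scale, it is 71% against 51%. Type I error is close to 5% for both analyses.

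**Counter-case: the truth is a step** (correlation 0.30 with the true grouping).

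- Step and cut both at the median: split 77.5%, continuous 57.2% (normal) or 64.6% (uniform). In simulation with a normal score, a cut at the sample median, which misses the true step slightly, gave 71% against 59%.
- Step at the top 30% of scores, cut at the median: the split keeps (0.3 − 0.15)² / (0.21 × 0.25) = 0.429, power 41.5%. The continuous score keeps 0.576 or 0.63, power 52.9% or 56.8%.

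**The case against.** The strongest reply is that the protocol has no analysis section. The sentence sits among data-recording instructions, nothing calls the split primary, and groups formed for description do not exclude a regression on the score. How an exposure is modelled is often left to an SAP, which was not available here. This stands as a limit: the point applies only if the split is the main analysis. It does not remove the point, because the protocol does commit to a split and states no alternative.

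Second, reference 7 may give an established cut-off, making high against low anxiety a deliberate and readable contrast. That is a reason to keep the contrast, though not to make it the only use of the score. Third, nothing in the protocol favours a linear relation over a threshold, and a step at the cut reverses the result. This is correct, and it is why linearity should be checked and the two-group comparison retained.

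Fourth, the headline powers assume a normal outcome, whereas most complications are scored 0-3. Simulated 0-3 outcomes (latent r = 0.30, normal score, Spearman against rank-sum) give about 55% continuous against 40% for a median split when the categories hold 70/15/10/5%. With 85/8/5/2% the figures are about 39% against 28%, or 32% with a 30/70 split. The direction holds, but the gain is about 7 to 15 points rather than 20, and absolute power is lower for these outcomes under either analysis.

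**Conclusion.** The point holds as an inexpensive improvement; it is not an error or contradiction in the protocol. If the two-group split is the main analysis and the relation is roughly linear, a median split costs the equivalent of 20 (80 − 60) to 29 (80 − 51) of the 80 patients, and a 20/80 split about 41 (80 − 39). At an assumed r of 0.30 with a normal outcome, this is a loss of about 13 to 20 power points at a median split. For a normal score it is about 13 to 20 points across r = 0.20 to 0.40. Confidence is medium, because the role of the split, the shape of the relation, the correlation and the group shares are all outside the document, and the advantage reverses for a true step at the cut.

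**What to change.** Before outcomes are examined, replace the sentence on grouping with text to this effect:

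> The preoperative score of [STAI-S or STAI-T, sponsor's choice] will be analysed as a continuous exposure, with linearity checked, for sore throat and the other complications. A comparison of two groups on the same scale, at [stated cut-off, from reference 7 if it supplies one], is secondary.

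Leave the blinded follow-up as it is. If an SAP already provides for this, only the protocol sentence needs to be aligned.

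The change needs no extra patients, visits or data. Its price is that the two-group contrast becomes secondary, linearity has to be examined, and a true step exactly at the cut would be detected less well than by the split.
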